10.2 OUTLINE OF STUDY PROCEDURES AND ASSESSMENTS

The first visit for this extension study is combined with the Month 6 visit of the main study. Therefore, the Month 6 assessments from the main study will not have to be duplicated at the start of the extension study. The study visit schedule is depicted in Figure 2 and the schedule of assessments is detailed in Appendix A and Appendix B.

* At the end of the 6-month follow-up, subjects with a BMD decrease from baseline of > 1.5% for lumbar spine and/or > 2.5% for total hip compared to main study baseline will have an additional DXA scan 6 months later.

Figure 2 : Schedule of Visits

All visits should take place at the end of the defined period (i.e. Month 7 visit should be scheduled at the end of Month 7, Month 8 visit should be scheduled at the end of Month 8, etc.). One month is defined as 28 days/4 weeks. All visit dates are calculated from the date the patient started treatment in the main study (Day 1 visit of 18-OBE2109-003 Edelweiss 3):

- Month 7 (Day 197), Month 8 (Day 225), Month 9 (Day 253), Month 10 (Day 281), Month 11 (Day 309) and Month 12 (Day 337) for the Treatment Period,
- Month 1 Extension FU (Day 365), Month 3 Extension FU (Day 421) and Month 6 Extension FU (Day 505) for the Follow-up Period.

A window of -3/+2 days is allowed for Month 7 visit, and of ± 3 days for each of the following visits during the Treatment Period. A window of ± 7 days/1 week is allowed for each visit scheduled during the Follow-Up Period.

The timing of events is shown in the Schedule of Assessments (Appendix A and Appendix B).

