10.2.1 Treatment Period

During the entire Treatment Period:

- the subject will use the same eDiary as during the main study. The eDiary should be completed daily, in the evening at approximately the same time, for use of provided/prescribed analgesics, uterine bleeding, pelvic pain, dyspareunia, dyschezia and daily function.
- the subject will take her daily dose of study medication at home except on the day of study visits where she will take her daily dose at site. There will be no IMP intake at the Month 12 visit. The last dose of study medication in this extension study will be the dose taken the day before Month 12 visit.
- the subject will be asked to bring her eDiary and her IMP kits at each visit to the site.
- the subject will receive contraception counselling at each visit.
- the subject will be provided/prescribed a limited quantity (as per Investigator's judgement) of standard doses of permitted analgesics as rescue medication for EAP for the duration of the study.
- the subject will receive calcium 500 to 1000 mg and vitamin D 400 IU supplementation which she will be advised to take daily (at least 4 hours from the intake of the study drug) until the end of the study. Intake should be recorded at each study visit in eCRF.
- AEs and concomitant medications will be recorded in the eCRF (excluding any provided/prescribed analgesics used for EAP will be recorded daily in the eDiary only).

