2. STUDY DESIGN

2.1. Introduction

This was a prospective, randomized, double-blind study. Subjects who completed the 6-month Treatment Period in the main study (18-OBE2109-003 - Edelweiss 3) were invited to enter the present extension study. Month 6 visit of the main study was a decision point for Subjects to either end treatment and enter a post-treatment follow up (part of the main study), or to opt for a 6-month treatment extension.

The extension study started at the Month 6 visit of the main study. Subjects were required to sign a specific informed consent form (ICF) for this extension study. Only subjects who completed the full 6-month Treatment Period in the main study and met the inclusion criteria were eligible for entry in the extension study.

All subjects received once daily linzagolix 75 mg alone (with ABT placebo) or 200 mg combined with ABT for 6 months. Subjects who received placebo during the main study were randomized to either linzagolix 75 mg alone (with ABT placebo) or linzagolix 200 mg with ABT. Subjects who received active treatment during the main study continued with the same treatment.

Linzagolix/placebo tablets were provided in monthly treatment kits, packaged, labelled and administered in the same manner to protect the blinded nature of the trial.

ABT/placebo treatments were supplied as 3-monthly kits, packaged, labelled and administered in the same manner to protect the blinded nature of the trial.

After end of treatment in the extension study (6-month Treatment Period: from Month 6 to Month 12), subjects entered a post-treatment Follow-Up Period of 6 months with no investigational medicinal product (IMP).

The total duration of the present extension study was to be 12 months.

A schematic of the study design is shown in Figure 1.

Figure 1: Study design

The schedule of assessments is in Appendix 9.6, further details available in the study protocol.

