5.2. Data Conventions

5.2.1. Last extension treatment administration date, End of extension Study date and Period definitions

The last extension treatment administration date will be defined as the date from the treatment termination reported in the extension period eCRF page. If this date is missing, the last date with a drug intake in the eDiary that is inferior or equal to Month 12 visit or the last available date with a drug intake in the eDiary if the subject discontinued the extension treatment will be used.

For subjects who entered the extension, the end of the extension study date will be the last assessment date in the extension study defined as last assessment recorded in the eCRF (excluding end date of adverse events and concomitant medications) or ediary date (excluding drug intakes recorded after last extension treatment administration date). This will not necessarily be the same date as last assessment date as recorded in the eCRF.

For each 28-day period prior to Month X (except Month 12), the end of the period will be defined as the Month X visit date. If subject discontinued prior to Month X, the end of the period will be the date from the treatment termination of extension period eCRF page or the last date with a drug intake in the eDiary if missing. If the subject missed the Month X visit (but did not discontinue), the subject might still have filled the diary during that time: the theoretical Month X date will be used to define the end of the 28-day period. The theoretical Month X is defined with respect to Day 1 as Month X= Day 1+ $28^{*}X$.

For the 28-day period prior to Month 12, the end of the period will be defined as the last extension treatment administration date.

Note:

For Adverse Events, Concomitant Medications and Daily diaries data collected on the Month 6 date will be part of the extension for subjects entering the extension study.

For Adverse Events, Concomitant Medications and Daily diaries, data collected on the Month 12 date will be part of the Extension Follow-up period for subjects entering the Extension follow-up period.

The extension treatment period will be defined as Month 6 up to (Month 12 date -1) or treatment discontinuation date.

The extension follow-up period will be defined as the Month 12 date or (treatment discontinuation date+1) up to the extension follow-up end date (for subjects who entered the extension follow-up).

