6.3. Study Population

6.3.1. Subject Disposition

A tabulation of subject disposition will be presented by treatment group and overall, for randomized subjects in the main study, including:

- Number of subjects randomized in the main study,
- Number of subjects who completed the main treatment period until Month 6
- Number of subjects who signed consent form for the extension study,
- Number of subjects who discontinued the study between informed consent for extension study and the first day of study drug in extension study,
- Number of subjects who received at least one dose of study drug in the extension study,
- Number of subjects who met discontinuation criteria at Month 6
- Number of subjects who completed the extension treatment period until Month 12
- Number of subjects who discontinued the extension treatment period prior to Month 12 (excluding those who met discontinuation criteria at Month 6), and reasons for extension treatment discontinuation
- Number of subjects who entered the extension follow-up period
- Number of subjects who discontinued the extension follow-up period, and reasons for the extension follow-up period discontinuation
- Number of subjects who completed the extension study (complete the extension treatment period and the extension follow-up period)

The number of subjects included in the extension study by country and by site will be also provided.

The number of subjects who completed each visit of the extension study will be summarized by treatment group and overall, for the Treatment Extension Analysis Set.

The following listings will be presented:

- Study completion information, including the reason for premature study withdrawal, if applicable;
- Inclusion/exclusion criteria;
- Subject inclusion in each of the analysis sets (Treatment Extension Analysis Set, Follow-up Extension Analysis Set, Extension Safety Analysis Set, Follow-up Extension Safety Set, Extension PD and Extension PK Analysis Sets) and reasons for exclusion for Treatment Extension Analysis Set and Per Protocol Extension Analysis Set.

6.3.2. **Demographic and Baseline Characteristics**

Baseline, demographic and medical history information will be analyzed by treatment group and overall, for the Treatment Extension Analysis Set and Extension Safety Analysis Set.

No formal statistical comparisons will be performed.

6.3.3. **Demographics**

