6.6.1. Adverse Events

All AEs recorded during the course of the study will be coded according to the MedDRA dictionary (26.0) and assigned to a system organ class (SOC) and Preferred Term (PT). The NCI-CTCAE (version 4.3) will be used to grade the severity of AEs.

The following definitions will be used for the analysis of adverse events (AEs). All analysis described below will be based on the Treatment Emergent Adverse Events (TEAEs), unless otherwise specified.

	Definition
Treatment emergent adverse event (TEAE)	AEs with a start date on or after the first dose of extension study drug through 30 days after discontinuation of study drug or Month 12 visit date, or any event that was present at Month 6 but worsened in intensity or was subsequently considered drug- related by the investigator through the end of the extension study
Treatment Related TEAE/AEs	LGX-related AEs, defined as having "definite, probable or possible" relationship to study drug ABT-related AEs, defined as having "definite, probable or possible" relationship to add-back therapy
Serious Adverse Events (SAEs)	Any AE with "Serious?" = Yes in the CRF "Adverse event" page.
Adverse Events Leading to Permanent Treatment Discontinuation	Any AE action taken = Drug Withdrawn in the CRF "Adverse event" page.
Adverse Events Leading to Death	Any AE with fatal outcome

Post-Treatment Adverse Events	Adverse events starting more than 30 days
	after end of treatment

TEAEs tables will be presented for the below periods/populations:

- Extension treatment period on Extension Safety Analysis Set
- Extension follow-up period on Follow-up Safety Analysis Set,
- Combined Extension treatment and follow-up period on Follow-up Safety Analysis Set
- Combined Main treatment period and Extension treatment period on Extension Safety Analysis Set:
- Combined Main treatment period and Extension treatment period on Safety Analysis Set
- Day 1 (from main study) to end of Extension follow-up period, or end of Main follow-up period for subjects not entering extension, on Safety Analysis Set

Post-treatment AEs tables will be presented for below periods/populations:

- Combined Extension treatment and follow-up period on Follow-up Safety Analysis Set
- Extension follow-up period on Follow-up Safety Analysis Set
- Day 1 (from main study) to end of Extension follow-up period, or end of Main follow-up period for subjects not entering extension, on Safety Analysis Set

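### SAP 6.6.1 sets a 30-day off-drug limit for new adverse events but none for events present at Month 6 that worsen, so late off-drug worsening is labelled treatment-emergent.

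*SAP*

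**What the plan says.** The definitions table in SAP 6.6.1 gives two routes to a treatment-emergent adverse event (TEAE).

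- **New events:** "AEs with a start date on or after the first dose of extension study drug through 30 days after discontinuation of study drug", with the Month 12 visit date as the alternative anchor.
- **Existing events:** any event "present at Month 6 but worsened in intensity or was subsequently considered drug- related by the investigator through the end of the extension study".

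The same table defines post-treatment AEs by onset alone: "Adverse events starting more than 30 days" after end of treatment.

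SAP 5.2.1 fixes what the end of the extension study means: "the end of the extension study date will be the last assessment date in the extension study". The disposition list in SAP 6.3.1 treats follow-up as part of completing the extension study, and SAP 2.1 describes that follow-up as six months without investigational product. Protocol 12.5 has AEs recorded up to the Month 6 extension follow-up (ExFU) visit.

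SAP 6.6.1 bases its AE analyses on TEAEs unless it says otherwise. It plans TEAE tables for the extension treatment period, the extension follow-up period, the two combined, main plus extension treatment, and Day 1 to the end of follow-up.

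**The concern.** The SAP draws a 30-day line between on-treatment and post-treatment experience and then leaves it off one limb of the TEAE definition. Two changes of equal clinical weight, on the same drug-free day, get different labels according to whether the event already existed at Month 6.

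AE incidence and severity are listed safety endpoints (SAP 3.3). A TEAE count that includes changes arising months after the last dose does not mean what its label says. The post-treatment tables meanwhile omit those changes, because they capture only events that start late.

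**Working it through.** **Inputs**

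- One month is 28 days and visits are counted from main-study Day 1 (Protocol 10.2).
- Month 12 visit: Day 337 (Protocol 10.2; SAP Table 1).
- Last dose: "The last dose of study medication in this extension study will be the dose taken the day before Month 12 visit" (Protocol 10.2.1).
- Last follow-up visit: "Month 3 Extension FU (Day 421) and Month 6 Extension FU (Day 505) for the Follow-up Period" (Protocol 10.2), with a window of ±7 days.
- Off-drug limit for new events: 30 days (SAP 6.6.1).

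**Reproducing the plan's dates**

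- Month 12 = 1 + 28 × 12 = Day 337.
- Month 6 ExFU = 337 + 168 = Day 505, which equals 1 + 28 × 18. Both agree with the protocol.

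**Where each limb closes**

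- Last dose = 337 − 1 = Day 336.
- New-event limb = 336 + 30 = Day 366, or 337 + 30 = Day 367 if counted from the Month 12 visit.
- Worsening limb = Day 505, which is 505 − 336 = 169 days after the last dose.
- Gap = 505 − 366 = 139 days, or 505 − 367 = 138 days from the Month 12 visit.
- With the ±7-day window (Day 498 to Day 512), the gap is 132 to 146 days from the last dose and 131 to 145 days from the Month 12 visit.

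**Early discontinuers.** Protocol 10.2.2.3 places their Month 6 ExFU visit 168 ± 7 days after last intake, so the gap is 168 − 30 = 138 days (131 to 145).

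**Upper end.** The optional BMD visit at about Day 674 does not widen the gap in practice, because AE recording stops at Month 6 ExFU.

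**Illustration.** Take Day 400, which is 400 − 336 = 64 days after the last dose. A headache present at Month 6 that goes from mild to severe on that day is a TEAE. A severe headache that starts on that day is a post-treatment AE.

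**Alternative parsing.** The closing phrase of the second limb might attach only to the causality clause. The worsening clause would then have no end date at all, so a 30-day limit is still absent.

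**Which tables are affected.** SAP 5.2.1 ends the extension treatment period the day before Month 12, or at discontinuation. A worsening dated after that falls naturally in the follow-up table, and also in the combined treatment-plus-follow-up and Day-1-to-end tables. It is called a TEAE in all of them. For women who do not enter follow-up, SAP 6.6.1 counts late AEs in the extension treatment period. The SAP does not say whether onset or worsening date places a worsened event in a period.

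**The case against.** The strongest reply is that the planned tables already divide experience by period. A reader might infer from the definition that the AE tables cannot separate on-drug from off-drug experience. That goes too far: there are separate TEAE tables for treatment and follow-up, and the tables that mix the two say so in their titles. What the period tables do not do is correct the label. A worsening on Day 400 is still reported as treatment-emergent, and the exception for women who do not enter follow-up puts late events into the treatment period.

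The second reply is that the rule is conservative. It can only attribute too much to drug, there is no concurrent placebo arm in the extension, no AE tests are planned, and all AEs are listed. This is fair and limits the consequence. It does not explain why one type of event is treated differently, and it ignores the matching shortfall in the post-treatment tables.

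The third reply concerns recording. Protocol 12.1.3 has worsened baseline conditions reported as AEs. If AEs ongoing at Month 6 were handled the same way, a late worsening would have its own record and start date. The documents do not settle this. If it is so, that record could meet both the TEAE and the post-treatment definitions, and the two would not be mutually exclusive.

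It is also true that one foreseeable off-drug change, return of endometriosis symptoms, is generally not an AE under Protocol 12.1.4.

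**Conclusion.** The asymmetry is real and follows from the text alone. On nominal dates the worsening limb stays open 139 days beyond the new-event limb (131 to 146 across visit windows and anchors). The first 30 days off drug are unaffected.

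Three stronger conclusions are tempting and not supported:

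- **A count of affected women.** The documents give no rate of AEs ongoing at Month 6 and no rate of later worsening, so any count would rest on invented inputs. The gap is 139 of 169 off-drug days, but that is a share of calendar days and not of events. Each woman also counts once per row, so a late worsening adds to the any-TEAE row only if she has no other TEAE. In the Phase 2b study, over 52 weeks, 154 of 176 women (87.5%) had one (Protocol 5.5.3). That is a different study, but it suggests little room in that row of the main-plus-extension tables.
- **Off-drug worsening sets the severity shown.** SAP 6.6.1 uses the most intense occurrence, so this can happen, but it depends on how worsening is recorded and which date assigns the period.
- **The later-causality criterion should be deleted.** It does admit events that neither began nor worsened in the extension. But the relatedness tables are restricted to TEAEs, so deleting it would drop from them an event present at Month 6 that was later judged related.

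The point is therefore a correctable inconsistency in a safety definition. No efficacy or inferential conclusion depends on it.

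**What to change.** Make three linked edits in the SAP.

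1. **TEAE definition, worsening limb (6.6.1).** Limit it to events present at Month 6 that worsen in intensity on or after the first extension dose and no later than the 30-day limit used for new events, with the same anchor.
2. **Post-treatment definition (6.6.1).** Extend it to events starting or worsening more than 30 days after end of treatment. Without this, late worsening would fall outside both definitions unless it had been entered as a new record.
3. **Period assignment (5.2.1 and 6.6.1).** State that a worsened event is placed by its date of worsening, and say how that date is obtained.

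Leave the later-causality criterion as it stands. If the sponsor does intend an open-ended worsening limb, the SAP should say so and show those events separately.

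The cost is slightly fewer TEAEs, correspondingly more post-treatment AEs, and one extra derived date or flag in the AE dataset. SAP 6.6.1 specifies severity and relatedness displays only for TEAEs, so reclassified events would lose those displays unless the post-treatment tables carry them. Data collection and clinical management do not change.

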- ECG: subjects who have a QTcF > 500 ms at the Month 6 assessment or increase > 60 ms from the highest value prior to the first dose in the main study

2. **Per Protocol Extension Analysis Set (PP EAS)**: All subjects from Treatment Extension Analysis Set, excluding those identified as having major protocol deviations that could potentially affect the efficacy assessments up to Month 12. Subjects will be analyzed according to randomized treatment.

3. **Follow-up Extension Analysis Set (FU EAS)**: All subjects from the main study who entered the extension study and received at least one dose of study drug with the exception of subjects whose Month 6 assessment subsequently met any of the discontinuation criteria, and who entered the Post-Treatment Follow-Up Period. Subjects will be analyzed according to randomized treatment.

4. **Extension Safety Analysis Set (ESAF)**: All subjects randomized into the extension study who received at least one dose of study drug irrespective of the treatment received. Subjects will be analyzed according to treatment received.

5. **Follow Up Safety Analysis Set (FU SAF)**: All subjects randomized into the extension study who received at least one dose of study drug irrespective of the treatment received, and who entered the Post-Treatment Follow-Up Period. Subjects will be analyzed according to treatment received.

6. **Extension Pharmacokinetic (PK) Set**: all subjects who were randomized and received active study medication in the main study, had no major protocol deviations impacting PK throughout the main study or extension and with available PK data. Subjects will be analyzed according to treatment received.

7. **Extension Pharmacodynamic (PD) Set**: all subjects who were randomized and received active study medication in the main study, had no major protocol deviations impacting PD throughout the main study or extension and with available PD data. Subjects will be analyzed according to treatment received.

In general, analyses of efficacy will be conducted using the TEAS, PP EAS (when specified) and FU EAS sets, analyses of safety will be conducted using the ESAF and FU SAF, and analyses of PK and PD will be conducted using the PK and PD Sets accordingly.

The actual treatment will be derived as follows, based on daily e-diary IMP intake data:

Treatment kits will be dispensed to the subjects as follows:

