All AEs tables will be presented for the below periods/populations:

- Day 1 (from main study) to end of Extension follow-up period, or end of Main follow-up period for subjects not entering extension, on Safety Analysis Set

Periods are defined in section 5.2

Tables based on Safety Analysis Set will use the following treatment groups, with the note that subjects can have a different time of treatment exposure (up to 6 months for subjects not in extension, up to 12 months for subjects entering extension):

- linzagolix 75 mg / linzagolix 75 mg
- linzagolix 200 mg with ABT / linzagolix 200 mg with ABT
- Placebo / linzagolix 75 mg (subject receiving placebo in main study and treated with linzagolix 75 mg in extension study)
- Placebo / linzagolix 200 mg with ABT (subject receiving placebo in main study and treated with linzagolix 200 mg with ABT in extension study)
- Placebo

If, for a subject not entering the Extension follow-up period, an AE occurs after Month 12-1 or treatment discontinuation, then the AE will be counted in the Extension treatment period.

For all study periods, an overall summary table will be prepared presenting, by treatment group, the number and percentage of subjects with

- any AE,
- any TEAE,
- any post-treatment AE (displayed only for the Extension follow-up period),
- Severe TEAE,
- any TEAE assessed by the Investigator as related to linzagolix ((definite, probable, or possible relationship),
- any TEAE assessed by the Investigator as related to add-back therapy ((definite, probable, or possible relationship),
- any TEAE leading to permanent discontinuation of IMP,
- any serious adverse event (SAE),
- any serious treatment emergent adverse event (Serious TEAE),
- any non-serious TEAE
- any serious treatment emergent adverse event (SAE) related to linzagolix,
- any serious treatment emergent adverse event (SAE) related to add-back therapy,
- any fatal TEAE (where outcome is "Fatal")

In these tabulations, each subject will contribute only once (i.e., via the most related occurrence or the most intense occurrence) to each of the incidence rates in the descriptive analysis, regardless of the number of episodes experienced.

Adverse events are summarized by subject incidence rates, therefore, in any tabulation, a subject contributes only once to the count for a given adverse event (SOC or preferred term).

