For the Extension treatment period, Extension follow-up period and combined Extension treatment and follow-up period, the number and percentage of subjects with any treatment-emergent adverse event, with any treatment-emergent adverse events assessed by the Investigator as related to treatment (definite, probable, or possible relationship), and with any treatment-emergent serious adverse event and with any treatment-emergent non-serious adverse event will be summarized by treatment group and overall, by SOC and PT. Tabulation by severity will also be made. In these tabulations, each subject will contribute only once (i.e., the most related occurrence or the most intense occurrence) to each of the incidence rates in the descriptive analysis, regardless of the number of episodes.

CRS-BS-TP-000005 V 2.0

The number of events will be also displayed for summaries on TEAE and for analysis of TEAE and non-serious TEAE by SOC and PT.

The ongoing status of each Adverse Event will be derived based on Adverse Event Outcome as the following:

AE Outcome	AE Ongoing Status
Fatal	No
Not recovered/not resolved	Yes
Recovering/resolving	Yes
Recovered/resolved	No
Recovered/resolved with sequelae	No
Unknown	Unknown
Missing	Missing

The ongoing status collected in eCRF will be ignored.

No formal hypothesis-testing analysis of adverse events incidence rates will be performed.

All adverse events occurring on study will be listed in subject data listings.

By-subject listings also will be provided for the following: Treatment Emergent Adverse event, serious Treatment Emergent adverse events; Treatment Emergent adverse events leading to permanent discontinuation of IMP and leading to permanent discontinuation of IMP leading to death.

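### The combined extension treatment plus follow-up TEAE tables omit dosed women who never enter follow-up, so they can understate some event rates and fail to reconcile with the treatment-period tables

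*SAP*

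**What the plan says.** SAP 6.6.1 lists the periods and populations for the TEAE tables. Three entries matter here:

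- "Extension treatment period on Extension Safety Analysis Set"
- "Combined Main treatment period and Extension treatment period on Extension Safety Analysis Set"
- "Combined Extension treatment and follow-up period on Follow-up Safety Analysis Set"

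SAP 4.1 defines the two sets. The Extension Safety Analysis Set (ESAF) is "All subjects randomized into the extension study who received at least one dose of study drug irrespective of the treatment received". The Follow Up Safety Analysis Set (FU SAF) adds a condition: women "who received at least one dose of study drug irrespective of the treatment received, and who entered the Post-Treatment Follow-Up Period".

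The combined period receives the full set of outputs. SAP 6.6.1 asks for an overall summary for every study period, with rows for severe, serious, discontinuation-related and fatal TEAEs. The tables by SOC and PT and by severity also include it: "For the Extension treatment period, Extension follow-up period and combined Extension treatment and follow-up period, the number and percentage of subjects".

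The same section anticipates dosed women who do not enter follow-up. The rule that begins "If, for a subject not entering the Extension follow-up period, an AE occurs after Month 12-1 or treatment discontinuation" assigns their late events to the extension treatment period.

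**The concern.** The combined tables start counting at the first extension dose, but membership is decided by something that happens after treatment: entry into follow-up. An adverse event can itself influence that entry. A woman who stops because of an event and then withdraws consent, is lost, or dies on treatment leaves both numerator and denominator, and all her on-treatment TEAEs go with her.

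The combined table is the only extension-only table that gives one count per woman over the whole TEAE window. SAP 6.6.1 extends that window to 30 days after treatment ends, while SAP 5.2.1 closes the extension treatment period on the day before Month 12 or at treatment discontinuation. For a woman who enters follow-up, the 30-day tail therefore falls in the follow-up period and is outside the treatment-period table. The tables that run through to the end of follow-up on the main-study Safety Analysis Set also contain main-study time and women who never entered the extension. No version of the combined extension table exists on ESAF.

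At stake are the rows for serious, discontinuation-related and fatal TEAEs in that table, and its agreement with the table for its own treatment-period component.

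**Working it through.** **Set logic.** FU SAF is ESAF restricted to women who entered follow-up. Let N be the ESAF size, E the number with a given TEAE, m the number who do not enter follow-up, and e the number of those m women who had the TEAE.

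- On ESAF: E / N
- On FU SAF: (E − e) / (N − m)

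The FU SAF figure is lower than the ESAF figure only if e/m exceeds E/N, that is, if non-entrants have the event more often than dosed women as a whole.

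**Inputs.**

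- N: up to 288 (Protocol 13.2). This reproduces: 450 × 0.80 = 360, and 360 × 0.80 = 288.
- TEAEs leading to withdrawal: 12 of 176 = 6.8% in the Phase 2b extension (Protocol 5.5.3), used as an assumption. 288 × 12/176 = 19.6, so E = 20.
- Any TEAE: 154 of 176 = 87.5% over 52 weeks in the same study, also an assumption. 288 × 0.875 = 252.
- Non-entry: no rate is given in either document, so a range is shown.

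**TEAEs leading to withdrawal.** ESAF gives 20/288 = 6.9%. If non-entry falls only on women with such an event (m = e):

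| Non-entrants | FU SAF |
|---|---|
| 0 | 20/288 = 6.9% |
| 5 | 15/283 = 5.3% |
| 10 | 10/278 = 3.6% |
| 15 | 5/273 = 1.8% |
| 20 | 0/268 = 0% |

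These rows are the extreme pattern. Two contrasting cases at 10% non-entry (m = 29):

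- Non-entry unrelated to the event: expected e = 29 × 20/288 = 2.0, giving 18/259 = 6.9%, unchanged.
- No non-entrant had the event: 20/259 = 7.7%, an overstatement.

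**Any TEAE.** Suppose every non-entrant had one. With 6, 14 or 29 non-entrants (2%, 5% or 10%), 252/288 = 87.5% becomes 246/282 = 87.2%, 238/274 = 86.9% or 223/259 = 86.1%. The movement is small for common events.

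**Death before follow-up entry.** One such death is 1/288 on ESAF and 0/287 on FU SAF, whatever the non-entry rate. A fatal TEAE that starts on treatment in a woman who enters follow-up and dies there can still appear.

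**Reconciliation.** With E = 20 and 10 of those women not entering, the treatment-period table on ESAF shows 20 women with a TEAE leading to withdrawal. The combined table, which spans a longer period, shows 10. Even with common events its N is lower than that of the treatment-period table.

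**The case against.** The strongest reply is that the affected rows are reported in full elsewhere. The extension treatment-period table on ESAF has the same overall summary, with the same severe, serious, discontinuation and fatal rows, and the same SOC/PT and severity tables. An event that leads to discontinuation or to death on treatment normally starts on treatment, so the 20/288 of the illustration would be printed there. The rule for late events of non-entrants puts those events in that table too. The events also appear in the main plus extension tables, in the Day 1 to end-of-follow-up tables on the Safety Analysis Set, and in the listings. All of this stands. A reader might infer that on-treatment deaths or discontinuation events could vanish from the study report; the documents do not support that.

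Second, Protocol 10.7.2 and SAP 2.4 and 5.4 direct women who discontinue during treatment into the 6-month follow-up. Non-entry is meant to be the exception, and the table above concentrates it entirely on women with the event. This also stands. A reader might infer that the combined rates are necessarily biased downward; the set logic shows that this depends on who fails to enter, which the documents do not tell us.

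Third, the post-treatment AE tables use the same set for the combined period, and it is tempting to change them too. That would be wrong. Post-treatment AEs start more than 30 days after treatment ends, when women who never entered follow-up are largely unobserved, and any late event they report is assigned to the treatment period. Adding them to the denominator would dilute the rate.

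Finally, the study is descriptive, with no formal hypothesis tests. That limits the consequences, but it does not make a table that is conditioned on a post-treatment event a sound summary of the on-treatment period.

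**Conclusion.** The point holds for the combined extension treatment plus follow-up TEAE tables only. Two consequences follow from the definitions alone: dosed women who never enter follow-up, and their on-treatment TEAEs, are outside these tables; and a death before follow-up entry cannot appear in them. It also follows that the combined table can show fewer women with an event than its own treatment-period component.

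Understatement of discontinuation, serious and fatal TEAE rates is conditional on non-entrants having more such events. That is plausible for discontinuation events but not established. Under the Phase 2b rate, with non-entry confined to affected women, 6.9% could become 5.3% with 5 non-entrants or 3.6% with 10. The any-TEAE row would move by at most 1.4 percentage points (87.5% − 86.1%) at 10% non-entry. The non-entry figures are assumptions throughout.

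This is a defect in how one group of tables is specified, not a gap in safety reporting. It is worth correcting because these are the only extension-only tables covering the full TEAE window, including the 30-day tail, and the correction is simple.

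**What to change.** In SAP 6.6.1, change the population of the combined extension treatment plus follow-up TEAE tables (overall summary, SOC/PT and severity) from the Follow-up Safety Analysis Set to the Extension Safety Analysis Set. Show the number entering follow-up by treatment group in the header; SAP 6.3.1 already derives it for the disposition table. Keep the Follow-up Safety Analysis Set for the follow-up-period tables and for the post-treatment AE tables.

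The cost is a short SAP edit and a different population flag in the same programs; no new data are needed. The small downside is that the combined table will then include women with no follow-up observation, which the header count discloses. If the population is left unchanged, the minimum is to title the tables as restricted to women who entered follow-up and to footnote the number excluded and their TEAEs.
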